4.1.1 Testing strategy to account for multiplicity considerations

A hierarchical testing procedure will be used to control the overall Type I error rate at 5% across the primary and key secondary endpoints. The variables will be tested sequentially in the following order using a 2-sided test and a 5% significance level:

- 1 Proportion of participants who are in complete remission while off OCS for ≥ 2 months at Week 36 (primary endpoint)
- 2 Proportion of participants who remain relapse-free up to Week 36 (key secondary endpoint)
- 3 Cumulative OCS exposure (mg/kg) from baseline to Week 36 (key secondary endpoint)
- 4 Change from baseline in BPDAI activity score at Week 36 (key secondary endpoint)
- 5 Change from baseline in BPDAI-Pruritus score at Week 36 (key secondary endpoint)
- 6 Cumulative OCS exposure (mg/kg) from baseline to Week 16 (key secondary endpoint)

If the treatment comparison for (1) is statistically significant, testing will proceed to (2). If the treatment comparison for (2) is statistically significant, testing will proceed to (3). If the treatment comparison for (3) is statistically significant, testing will proceed to (4). If the treatment comparison for (4) is statistically significant, testing will proceed to (5). If the treatment comparison for (5) is statistically significant, testing will proceed to (6). If, at any point in this hierarchy, a null hypothesis cannot be rejected at the 5% significance level in favour of benralizumab, further testing will stop, and no subsequent null hypotheses will be rejected.

4.1.2 Stratification and subgroup variables

Statistical models will include stratification factors to properly handle the possible variation of treatment effect within the strata, as detailed in Section [4.2](#).

Exploratory analyses will be also carried out to explore the uniformity of the detected overall treatment effect across key, pre-defined, subgroups. These analyses will focus on the primary endpoint, and they may be performed on key secondary endpoints if deemed appropriate. If a small number of participants are in a subgroup, only descriptive statistics will be reported, and formal comparisons might not be performed.

The following stratification and/or subgroup variables are defined:

Disease severity (Moderate, Severe)

The BPDAI activity score at baseline will be used to assess disease severity, whereby participants with a score greater than or equal to 56 points will be classified as severe.

Time of BP diagnosis (Participants newly diagnosed, Participants previously diagnosed and relapsing)

A participant is defined as newly diagnosed if the participant is enrolled during the first episode of BP, and this episode hasn't been controlled prior to the study. The number of relapses in the past 2 years as collected in the eCRF is equal to zero.

A participant is defined as previously diagnosed and relapsing if the participant is enrolled during a relapse of BP. In this case the number of relapses in the past 2 years as collected in the eCRF is ≥ 1 .

Time of BP diagnosis and recurrence treatment (Participants newly diagnosed, Participants previously diagnosed and relapsing on OCS, Participants previously diagnosed and relapsing off OCS)

Participants newly diagnosed will be identified as detailed above, while participants previously diagnosed will be further classified into:

Previously diagnosed and relapsing on OCS, if the participant most recent relapse occurred whilst the participant was on OCS, during tapering, or within 2 months of tapering off OCS.

Previously diagnosed and relapsing off OCS, if the participant most recent relapse occurred whilst the participant had been off OCS for more than 2 months.

Age group (at informed consent, < 65 years, ≥ 65 years and < 75 years, ≥ 75 years)

Age will be derived from the date of informed consent - date of birth, rounded down to the nearest integer. For participants in countries where date of birth is not recorded, the age as recorded in the eCRF will be used.

Gender (male, female)

Race (White, Asian, Other)

Region (Europe, North America, Rest of World)

OCS dose at randomization (≤ 0.5 mg/kg/day, > 0.5 mg/kg/day; if suitable distribution of data)

Baseline blood eosinophils ($<$ median, \geq median)

OCS dose at disease control (≤ 0.5 mg/kg/day, > 0.5 mg/kg/day; if suitable distribution of data)

OCS dose at disease control will be calculated for each participant as the dose recorded by the Investigator as per Section 3.1.5.1 on the day before the clinical assessment of disease control.

Stratification and subgroup variables will be based on eCRF data, and not data entered in IxRS. If eCRF data is missing for disease severity or time of BP diagnosis, the IxRS data will be used in the analysis.

4.2 Analysis methods

4.2.1 Participant disposition

Participant disposition will be summarized using the all participants analysis set. The total number of participants will be summarized for the following groups: those who enrolled and

those who were not randomized (and reason). The number and percentage of participants within each treatment group will be presented by the following categories: randomized, received treatment with study drug, completed treatment with study drug, discontinued treatment with study drug (and reason), discontinued treatment with study drug but completed study follow-up, completed the double-blind period, and withdrawn from study (and reason). This will be presented for both the double-blind treatment period and the extension period.

Screen failure information will be listed for the all participants analysis set.

The number of participants remaining on treatment, participants discontinued IP but still in study follow-up, and participants who withdraw from the study will be summarized by treatment group and scheduled visit, separately for participants in the FAS.

The number of participants randomized by country and centre will also be summarized by treatment group in the FAS.

4.2.2 Demography data and participant characteristics

Demography and baseline characteristics will be summarized by treatment group and overall in the FAS, using frequency and percentages (for categorical variables) and descriptive statistics of n, mean, standard deviation, median, minimum, and maximum, and where appropriate first quartile and third quartile (for continuous variables). If there are major differences in the number of participants between the FAS and safety analysis set, these summaries will be repeated for the safety analysis set. These summaries will be presented for reporting of the double-blind treatment period at primary DBL.

Various baseline characteristics will also be summarized. These include participant characteristics (ie, age at informed consent [as continuous and categorical variable in 3 categories < 65 years, ≥ 65 years and < 75 years, ≥ 75 years], weight, height, BMI, gender, ethnicity, race, region) and disease characteristics (ie, disease severity, time of BP diagnosis, current active disease duration at screening [as collected in the eCRF in 5 categories ≤ 1 month, >1-≤ 3 months, >3-≤ 6 months, >6-≤ 12 months, > 12 months], number of BP relapses the last 2 years before screening [as collected in the eCRF in 4 categories 0, 1, 2, ≥ 3], clinical presentations [including presence of blisters, pruritus, erosions, erythema, urticaria plaques], anatomic location, OCS dose at randomization [as continuous and categorical variable in 4 categories ≤ 0.25 mg/kg/day, > 0.25 mg/kg/day and ≤ 0.50 mg/kg/day, > 0.50 mg/kg/day and ≤ 0.75 mg/kg/day, > 0.75 mg/kg/day], baseline blood eosinophil count [as continuous and categorical variable in 4 categories < 150 cells/µL, ≥ 150 cells/µL and < 300 cells/µL, ≥ 300 cells/µL and < 450 cells/µL, ≥ 450 cells/µL], baseline total serum IgG directed against auto-antigens BP-180, baseline total serum IgG directed against auto-antigens BP-230).

Age will be derived from the date of informed consent-date of birth, rounded down to the nearest integer. For participants in countries where date of birth is not recorded, the age as recorded in the eCRF will be used.

Medical and surgical histories will be coded using the most recent version of the MedDRA that will have been released for execution at AstraZeneca/designee per the Data Management Plan and will be summarized by MedDRA Preferred Term (PT) within MedDRA System Organ Class (SOC).

4.2.3 Prior and concomitant medications

The frequency and percentage of participants reporting usage of prior medications, those reporting use of allowed concomitant medications, and those reporting usage of restricted concomitant medications (refer to CSP Section 6.5.2) will be summarized by treatment group and overall. OCS will be included in the above summaries, but also reported separately. The frequency and percentage of participants reporting OCS usage as rescue medication will be summarized by treatment group and overall for scheduled visits.

The concomitant medications will be summarized over the double-blind period and over the OLE period, respectively. A summary table of background medications at baseline will also be provided.

Concomitant medications will be classified according to the WHO Drug Reference List dictionary. The summary tables will present data by generic term within Anatomical Therapeutic Chemical code.

4.2.4 Study treatments

Exposure to IP administration will be calculated in days as:

$$(Last\ dose\ date\ of\ IP - first\ dose\ date\ of\ IP + 1)$$

and will be summarized descriptively by treatment group for the safety analysis set. Exposure will be computed overall, during double-blind period and during OLE.

The number and percentage of participants with duration of IP administration in each of the following categories will also be summarized:

<16 weeks
≥16 weeks and <24 weeks
≥24 weeks and <36 weeks
≥36 weeks and <52 weeks
≥52 weeks and <76 weeks
≥76 weeks and <104 weeks
≥104 weeks

4.2.5 Compliance

Study treatment compliance with IP administration will be summarized descriptively by treatment group for the FAS and calculated as:

$(\text{Total doses administered} / \text{total doses expected}) \times 100.$

The total number of doses expected includes all visits with protocol scheduled IP administration on or before a participant's IP discontinuation or treatment completion date.

Treatment compliance during the double-blind period will be calculated using the sum of administrated injection doses divided by the total number of injection doses until Week 36/IPD visit (excluding the first dose of OLE IP).

4.2.6.2 Subgroup analyses for the primary outcome variable

To explore the uniformity of the detected overall treatment effect on the primary efficacy variable, subgroup analyses and statistical modelling including testing for interaction between treatment and covariates will be performed for the stratification factors listed in Section [4.1.2](#).

For each of the subgroup factors in turn, a separate logistic regression model will be fitted using the same model terms as used for the primary analysis (described in Section [4.2.6.1](#)), with additional terms for the subgroup main effect and the treatment by subgroup interaction. Disease severity and time of BP diagnosis will not be a covariate when used as subgroup. If any model does not converge, respective sub-groups may be collapsed appropriately.

Similar statistics will be presented for each subgroup as for the primary analysis. The p-value for the interaction term will be presented in the analysis summary tables and forest plots will present the odds ratio with confidence intervals for each level of the subgroups.

Results for the subgroups based on OCS dose at disease control will be reported separately, since OCS dose at disease control is not a baseline variable.

It is important to note that the study has not been designed or powered to assess efficacy within any of these pre-defined subgroups, and as such these analyses are considered as exploratory.

4.2.7 Key Secondary efficacy outcome variables

4.2.7.1 Proportion of participants who remain relapse-free up to Week 36

The proportion of participants who remain relapse-free up to Week 36 will be analyzed as a binary response variable, where participants who remain relapse-free throughout the study up to Week 36 will be considered responders, but otherwise participants will be considered non-responders. More details on derivation rules and intercurrent events are given in Section 3.3.1.

The null hypothesis is: odds of responding on brentuximab is equal to the odds of responding on placebo (this can be interpreted as there is no difference in the proportion of participants who remain relapse-free up to Week 36 between brentuximab and placebo). Whereas, the alternative hypothesis is: the odds of responding on brentuximab is not equal to the odds of responding on placebo. That is:

$$H_0: \text{Odds ratio (brentuximab 30mg / Placebo)} = 1$$

$$H_1: \text{Odds ratio (brentuximab 30mg / Placebo)} \neq 1$$

The proportion of participants who remain relapse-free up to Week 36 will be analyzed using the same method described for the primary endpoint as detailed in Section 4.2.6.1

As a supportive analysis to the proportion of participants who remain relapse-free, time to first BP relapse will be analysed using a log-rank test (performed using the LIFETEST procedure with a TEST statement) stratified by baseline disease severity and time of BP diagnosis. A p-value, corresponding to a 2-sided test, will be presented to compare the brentuximab and placebo treatment groups.

The hazard ratio and its 95% CI will be estimated from a stratified Cox Proportional Hazards model with baseline disease severity and time of BP diagnosis as covariates. 95% CI will be calculated using a profile likelihood approach.

The tie handling recommended approach for the log-rank test is the Breslow method and for the Cox proportional hazards model is the Efron method.

An unadjusted analysis (an unstratified log-rank test and a Cox proportional hazards model adjusting for treatment group only) may be conducted as a sensitivity analysis. If there are convergence issues when the study is unblinded (for example due to a stratum experiencing zero events), an unadjusted analysis will replace the analysis outlined above.

The median time to first relapse will be estimated from the Kaplan-Meier curves for the benralizumab and placebo treatment groups, where calculable.

4.2.7.2 Cumulative OCS exposure (mg/kg) from baseline to Week 36 and from baseline to Week 16

Cumulative OCS exposure (mg/kg) from baseline to Week 36 and from baseline to Week 16 will be calculated for each participant over 4 weekly intervals. More details on derivation rules and intercurrent events are given in Section 3.3.2.

The null hypothesis is: the mean for benralizumab is equal to the mean for placebo. Whereas, the alternative hypothesis is: the mean for benralizumab is not equal to the mean for placebo. That is:

$$H_0: \text{Difference in means (benralizumab} - \text{placebo}) = 0$$

$$H_1: \text{Difference in means (benralizumab} - \text{placebo}) \neq 0$$

This endpoint will be analysed by a MMRM model.

The cumulative exposure over the 36 (and 16) weeks will be estimated as the sum over the relevant 4-week periods from the MMRM model. This analysis method was selected to utilize all available data in the situation of any participants dropping out prior to 36 weeks. This ensures that any such participants can still contribute to the analysis for the period they remain in the study, without needing to make potentially implausible imputation assumptions around future OCS exposures in these situations (eg, carrying forward a high last observation of 0.75 mg/kg/d, which would not be a feasible dose to maintain for a 36-week period).

The model will include cumulative OCS exposure (mg/kg) as the dependent variable; treatment, 4 weekly interval, baseline disease severity and time of BP diagnosis as categorical covariates, treatment-by-4 weekly interval as an interaction term.

An unstructured variance-covariance matrix will be used to model within-participant errors, and the Kenward-Roger approximation will be used to estimate denominator degrees of freedom and to adjust standard errors. If the model fails to converge, alternative variance-covariance models will be tried in the following order: Toeplitz, first-order regressive, compound symmetry.

For each 4 weekly interval and the whole of the 36-week treatment period, and for the initial 16-week treatment period, the model will be used to estimate the mean cumulative OCS exposure (mg/kg) for each treatment group and the difference versus placebo, with corresponding 95% confidence limits.

Results will be presented in terms of least square (LS) means of cumulative OCS exposure (mg/kg), treatment differences in LS means of cumulative OCS exposure (mg/kg), 95% CI and p-values for all scheduled visits. The cumulative OCS exposure (mg/kg) at Week 36 and Week 16 will be of primary interest. The LS means will be calculated using the OM option in the LSMEANS statement and the treatment-by-visit interaction to provide a LS means estimate for each scheduled visit. The LS means with 95% CIs will also be presented for each treatment group by scheduled visit.

P-values, corresponding to 2-sided tests, will be presented to compare the benralizumab and placebo treatment groups for each interval, including the whole of the 36-week treatment period and the initial 16-week treatment period.

The following SAS code is given as an example:

```
lsmestimate Treatment * 4WeeklyInterval  
  
'Treatment 1: 16 weeks' 0 0 0 0 0 0 0 0 0  
                      1 1 1 1 0 0 0 0 0,  
'Treatment 0: 16 weeks' 1 1 1 1 0 0 0 0 0  
                      0 0 0 0 0 0 0 0 0,  
'Diff: 16 weeks'    -1 -1 -1 -1 0 0 0 0 0  
                      1 1 1 1 0 0 0 0 0,  
'Treatment 1: 36 weeks' 0 0 0 0 0 0 0 0 0  
                      1 1 1 1 1 1 1 1 1,  
'Treatment 0: 36 weeks' 1 1 1 1 1 1 1 1 1  
                      0 0 0 0 0 0 0 0 0,  
'Diff: 36 weeks'    -1 -1 -1 -1 -1 -1 -1 -1 -1  
                      1 1 1 1 1 1 1 1 1  
/ om cl;
```

To support this analysis, observed means will be summarized using descriptive statistics by treatment group and 4 weekly interval, including the whole of the 36-week treatment period and the initial 16-week treatment period. Observed means will be also plotted by treatment group and 4 weekly interval.

To explore the uniformity of the detected overall treatment effect, the model might also be fitted considering OCS dose at randomization and its interaction with treatment as additional covariates.

The set of intercurrent events for this estimand and the imputation approach are detailed in Section 3.3.2. Since any BP relapses are expected to be treated with OCS (which is incorporated in the endpoint definition), the use of restricted medications which would result in exclusion of data beyond that point are expected to be infrequent. Therefore, the amount of missing data is expected to be low and is considered not likely to impact the results.

Sensitivity analyses might be conducted based on different missing data mechanism assumptions, including those expected to be more conservative, such as MNAR, to explore the robustness of any treatment effect, if the amount of missing data warrants further investigation. This might include utilizing multiple imputation approaches including the dropout reason-based multiple imputation where dropouts related to treatment are imputed using a jump to reference approach. Details using multiple imputation techniques are specified in Appendix 8.1.

Cumulative actual OCS exposure (mg) will be also summarized in an exploratory way using descriptive statistics by treatment group and 4 weekly interval, including the whole of the 36-week treatment period and the initial 16-week treatment period.

Daily OCS dose (mg/kg/day) will be also summarized in an exploratory way using descriptive statistics by treatment group and weekly interval from Week 2 to Week 36.

4.2.7.3 Change from baseline in BPDAI activity score at Week 36

The change from baseline in the total BPDAI activity score at Week 36 will be analysed by an ANCOVA model. More details on derivation rules and imputation rules to handle intercurrent events are given in Section 3.3.3.

The null hypothesis is: the mean for benralizumab is equal to the mean for placebo. Whereas, the alternative hypothesis is: the mean for benralizumab is not equal to the mean for placebo. That is:

$$H0: \text{Difference in means (benralizumab} - \text{placebo}) = 0$$

$$H1: \text{Difference in means (benralizumab} - \text{placebo}) \neq 0$$

The model will include change from baseline at Week 36 as the dependent variable, baseline BPDAI activity score as a continuous covariate and treatment and time of BP diagnosis as categorical covariates. Only patients with baseline and at least one post-baseline BPDAI activity score will be included in the model.

The model will be used to estimate, in terms of LS means, the mean change from baseline at Week 36 for each treatment group and the difference versus placebo, with corresponding 95% confidence limits. A p-value, corresponding to a 2-sided test, will be presented to compare the benralizumab and placebo treatment groups.

For participants who receive medications deemed to be intercurrent events as per Section 3.1.5.2 or need to increase their OCS dose as a rescue therapy will be imputed using a last observation carried forward (LOCF) method, as detailed in Section 3.3.3.

For participants who withdraw from the study without having rescue or restricted medications, missing BPDAI activity score at Week 36 will be imputed using multiple imputation based on outcome of participants who don't have rescue/restricted medication use. The same approach will be applied to those participants with missing data at Week 36 for any other reason. Distributions will be modelled considering treatment group, time of BP diagnosis and values of BPDAI activity score observed at baseline and prior to the withdrawal/occurrence of intercurrent events.

Specifically, for a participant with missing observations after visit t, imputed observations value at visit t+n will be based on a model estimated from all participants who have an outcome observed at visit t+n conditioning on that participant's outcomes up to and including visit t.

Then, the overall estimate of treatment effect is obtained by using Rubin's rules [Rubin 1987] to combine the imputed outcomes using the ANCOVA model above specified.

In summary, the pattern mixture models will be implemented by multiple imputation via the following steps;

Step 1: Non-monotone missing data (usually relatively infrequent) will be imputed using the MCMC statement of SAS PROC MI under the MAR assumption. The following variables will be included in the imputation model: treatment group, time of BP diagnosis and BPDAI activity score from baseline to Week 36. Note: Dummy variables will be used for treatment and time of BP diagnosis. This will create a monotone missing pattern in the dataset within each treatment group. This step will create 100 imputed datasets.

Step 2: For participants who withdraw from the study without having rescue or restricted medications the values for each pattern will be imputed via the sequential regression method, using the MONOTONE REG statement of SAS PROC MI. The imputation model will be estimated from the observed data in participants without intercurrent events or need to increase their OCS dose as a rescue therapy and it will be used to impute missing observations in both treatment groups using the MNAR statement of SAS PROC MI. The following variables will be included in the imputation model: treatment group, time of BP diagnosis and BPDAI activity score from baseline to Week 36.

Step 3: For participants who receive medications deemed to be intercurrent events or need to increase their OCS dose as a rescue therapy the missing values for each pattern will be replaced by the last observation carried forward.

Step 4: The imputed data from Step 1, Step 2 and Step 3, along with observed data will be combined to create 1000 complete dataset which will then be analysed using the main ANCOVA statistical model.

Step 5: The estimates from multiple imputed datasets will be combined using Rubin's combination rules for statistical inference (using PROC MI ANALYZE).

The seed used will be 88281 for both steps 1 and 2.

To support this analysis, observed means and mean changes from baseline will be summarized at each scheduled visit up to Week 36 using descriptive statistics by treatment group. The same descriptive approach will be used to summarize results for the total BPDAI damage score.

To explore the uniformity of the detected overall treatment effect, the model might also be fitted considering baseline variables and their interaction with treatment as additional covariates.

In addition, the cumulative distribution function of absolute changes from baseline in BPDAI activity score at Week 36 will also be plotted, to allow the treatment difference at various response thresholds to be explored. Responder analyses using minimal clinically important differences presented in the literature ([Wijayanti et al 2017](#)) may be presented, if appropriate.

4.2.7.4 Change from baseline in BPDAI-Pruritus score at Week 36

The change from baseline in the BPDAI-Pruritus score at Week 36 will be analysed by a ANCOVA model. More details on derivation rules and intercurrent events are given in Section [3.3.4](#).

The statistical analysis described in Section [4.2.7.3](#) for BPDAI activity score will be carried out for this endpoint using 88381 as the seed. In the MI models however, baseline disease severity will be added as categorical covariate.

To support this analysis, observed means and mean changes from baseline will be summarized at each scheduled visit up to Week 36 using descriptive statistics by treatment group.

In addition, the cumulative distribution function of absolute changes from baseline in BPDAI activity score at Week 36 will also be plotted, to allow the treatment difference at various response thresholds to be explored.

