The model will include cumulative OCS exposure (mg/kg) as the dependent variable (calculated for each participant over 4 weekly intervals up to Week 36); treatment, 4 weekly interval, baseline disease severity and time of BP diagnosis as categorical covariates; treatment-by-4 weekly interval as an interaction term. The inclusion of baseline OCS dose as a covariate will also be considered. An unstructured variance-covariance matrix will be used to model within-participant errors, and the Kenward-Roger approximation will be used to estimate denominator degrees of freedom and to adjust standard errors. (If the model fails to converge, alternative variance-covariance models will be tried in the following order: Toeplitz, first-order regressive, compound symmetry.) For each 4 weekly interval and for the sum of the 4-weekly intervals over the whole of the 36-week treatment period, and for the sum of the 4-weekly intervals over the initial 16-week treatment period, the model will be used to estimate the mean cumulative OCS exposure (mg/kg) for each treatment group and the difference versus placebo, with corresponding 95% confidence limits. P-values, corresponding to 2-sided tests, will be presented to compare the benralizumab and placebo treatment groups for each interval, including the whole of the 36-week treatment period and the initial 16-week treatment period.

To support this analysis, observed means will be summarized using descriptive statistics by treatment group and each 4 weekly interval, are for the whole of the 36-week treatment period and the initial 16-week treatment period.

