1.3 Number of subjects

Approximately 140 participants will be enrolled/screened in order to achieve approximately 100 eligible study participants randomly assigned to study intervention.

The sample size calculation was derived for the primary endpoint, the proportion of participants who are in complete remission while off OCS for ≥ 2 months at Week 36.

Approximately 50 participants are needed per treatment group to detect a 30% difference between benralizumab and placebo with 85% power. The calculation is based on a 2-sided test and a 5% significance level and assumes a response rate of 50% for benralizumab and 20% for placebo.

There is limited evidence currently available from completed comparative BP trials to date to base the study size assumptions on. However, a mepolizumab Phase 2 trial with a similar participant population, design, and steroid taper rate reported a low proportion of patients relapse free up to 36 weeks (20% versus 33% for mepolizumab versus placebo; [Simon et al 2020](#)). From this study, the assumption that an expected remission rate off steroids at Week 36 would be low, at most 20%, was extrapolated. A 30% improvement in this remission rate was recommended by a panel of BP experts to be at the lower end of what may be clinically meaningful, and so was considered to be a conservative assumption.

A non-binding interim futility analysis will be performed by an Independent Data Monitoring Committee (IDMC) when approximately 36 randomized participants (ie, when approximately 36% of the total amount of statistical information is available) have had the opportunity to complete at least 36 weeks of follow-up. By conducting the interim analysis, the overall power will not be affected substantially. Full details are provided in Section [5](#).

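### If the unstructured MMRM for cumulative OCS does not converge, the named fallback covariances give unreliable standard errors for the 36- and 16-week sums; a robust standard error should be pre-specified

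*SAP*

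**What the plan says.** SAP 4.2.7.2 models OCS exposure (mg/kg) in nine 4-week intervals. The terms are treatment, interval, treatment-by-interval, baseline severity and time of diagnosis. The covariance is unstructured, and "the Kenward-Roger approximation will be used to estimate denominator degrees of freedom and to adjust standard errors". The tested quantities are sums of interval differences: all nine for Week 36 and the first four for Week 16, as the example SAS contrasts show.

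On non-convergence the SAP says that "alternative variance-covariance models will be tried in the following order: Toeplitz, first-order regressive, compound symmetry". The second structure is read here as AR(1), and the third is shortened to CS. Protocol 9.4.2.2 has the same contingency: "If the model fails to converge, alternative variance-covariance models will be tried in the following order", followed by the same three structures. Neither document names a heterogeneous-variance form or an empirical standard error.

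In SAP 4.1.1 these endpoints are tests 3 (Week 36) and 6 (Week 16): "The variables will be tested sequentially in the following order using a 2-sided test and a 5% significance level". Test 3 gates tests 4 to 6.

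**The concern.** Toeplitz, AR(1) and CS, in the forms named, give every interval the same variance and let correlation depend at most on lag. The OCS course does not look like that. Participants start at a common 0.5 mg/kg/day, with increases allowed (Protocol 4.1.2). They then taper with the aim of being off OCS 4 to 5 months from randomization (Protocol 6.5.1), and OCS is raised or restarted at relapse. Spread should therefore be small at first and larger as up-dosing and taper timing differ. Late on it should depend on how many participants relapse and how much they are re-dosed.

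Because each test statistic is a sum over intervals, an error in the covariance passes straight into its standard error. Kenward-Roger adjusts for small samples within the assumed structure and takes that structure as correct. The MNAR sensitivity analysis in SAP 8.1.5 refits the same MMRM, so it would not reveal the problem. What is at stake is the 5% level of two gated tests if a fallback is used. If the standard error is overstated, the cost is power instead.

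**Working it through.** **The plan's own figure.** SAP 1.3 states "Approximately 50 participants are needed per treatment group to detect a 30% difference between benralizumab and placebo with 85% power", with 50% against 20% and a 2-sided 5% test. This reproduces: 84.8% with a continuity correction and 85.3% for Fisher's exact test (89.4% uncorrected). It concerns the primary endpoint only. Neither document gives an SD, correlation or power for cumulative OCS, so everything below rests on assumed courses and is given as ranges.

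**Inputs from the documents.** About 50 per arm (SAP 1.2.2); nine intervals, so 9 × 10 / 2 = 45 unstructured covariance parameters; 0.5 mg/kg/day at the start, which is 0.5 × 28 = 14 mg/kg per interval; taper of 20% per week to 10 mg/day, then 2.5 mg every other week (Protocol 6.5.1); relapse 27% to 53% (Protocol 2.2.1). The 20% relapse-free rate cited in Protocol 9.2 implies up to 80%.

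**Assumed.** Body weight, time to control, share up-dosed, and timing and size of re-dosing at relapse. Relapse was varied from 27% to 80%.

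**Formula.** Let c be nine ones (36 weeks), or four ones then five zeros (16 weeks). Let S be the true covariance and V the fallback fitted to it by likelihood. With complete data the actual level is

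2 × [1 − Φ(1.96 × √(c′Vc / c′Sc))].

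These level calculations used treatment-by-interval means without the two stratification covariates.

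**A check by hand.** One assumed course, with more early up-dosing and mild re-dosing, has interval SDs 2.73, 5.67, 5.47, 3.00, 1.62, 1.36, 1.24, 1.24, 1.24. The variances sum to 87.6, so a common variance is about 87.6 / 9 = 9.73 (SD 3.12). The first four average 78.5 / 4 = 19.63.
- If intervals were uncorrelated, the standard-error ratio for the 16-week sum is √(9.73 / 19.63) = 0.70, a level of 16.8%.
- If perfectly correlated, it is 4 × 3.12 / 16.87 = 0.74, a level of 14.7%.

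The full fits for this course, which also estimate the correlations, give 20.5% (Toeplitz), 20.4% (AR(1)) and 25.5% (CS). If variance is concentrated late instead, the same pooling overstates the early variance and the 16-week test becomes conservative.

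**Large-sample levels, complete data, all assumed courses (nominal 5%).**

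| Structure | 36-week sum (test 3) | 16-week sum (test 6) |
|---|---|---|
| Toeplitz (first fallback) | 5.3-9.8% | 0.7-21% |
| AR(1) | 1.5-5.5% | 0.5-20% |
| CS | 5.0% | 1.9-25% |

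By the formula, 9.8% corresponds to a model standard error 0.84 of the true one, 21% to 0.64, and 0.7% to 1.38. CS is exact for the 36-week sum with complete data because its likelihood fit reproduces the variance of the total.

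**With 15% dropout by Week 36** (assumed, one family of courses): Toeplitz 36-week 6.5-6.6%; CS 36-week 5.4-5.8%.

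**Finite-sample checks at 50 per arm.** Toeplitz 36-week 6.4% (1,500 runs) and 5.8% (1,000 runs, Monte Carlo SE about 0.7 points); 16-week 5.9% and 4.6%. CS 16-week 9.2% and 9.0%. The unstructured SE, which the sandwich SE matches when data are complete, gave 5.0% for both sums (4,000 runs).

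**How likely is the trigger?** Unstructured REML with the planned terms was fitted to simulated courses for 100 participants, in purpose-written code rather than SAS. It converged in 400 of 400 runs at 0-15% dropout and in 199 of 200 at 25%. Condition numbers across the simulated covariances were about 34 to 100, so they were not near-singular.

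**The case against.** The strongest reply is that this is a remote contingency. The planned model holds about 5%, missing OCS data are expected to be few (SAP 4.2.7.2), and simulated fits almost always converged. At a failure rate of 1%, even a 25% level under the fallback adds only 0.01 × (25 − 5) = 0.2 points to the unconditional level. The fallback order is fixed in advance and identical in both documents, so no choice is left until after unblinding. For test 3, which does the gating, the finite-sample Toeplitz excess is about one point, and 5.8% cannot be told apart from 5% at that number of runs. All of this stands, and it keeps the point minor.

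A reader might infer more than the documents support:
- **That the planned analysis inflates error.** It does not; only the fallback is affected.
- **That non-convergence is to be expected** because the first interval is almost constant. The documents give no failure rate. They allow higher starting doses and earlier or faster tapering, and the simulated first-interval SDs were well above zero.
- **That the level is always inflated.** For the 16-week sum the direction depends on whether early or late intervals vary more. AR(1) is mostly conservative for the 36-week sum.
- **That overall Type I control fails generally.** Test 3 is reached only if tests 1 and 2 reject, and test 6 only if tests 1 to 5 reject. If the primary null is true, familywise error stays at 5% whatever covariance is used for OCS.

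The reply does not show that the fallback rule is valid when it is invoked.

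**Conclusion.** The point holds as a conditional one. If the unstructured fit fails and a listed fallback is used with Kenward-Roger, the standard errors for the 36- and 16-week sums are unreliable, and tests 3 and 6 are not held at 5%. For test 3 under Toeplitz, every assumed course gave a large-sample level above 5%, though the excess is modest at 50 per arm. For test 6 the possible error is much larger and its direction unknown. The equal-variance assumption follows from the structures named, and its implausibility from the protocol's own OCS course; the sizes rest on assumed SDs and correlations. The probability of using a fallback is unknown and probably low. Familywise error is touched only in configurations where the earlier nulls are false and the OCS null is true. Severity: minor.

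**What to change.** Add to SAP 4.2.7.2, before unblinding:

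*If a structure other than unstructured is used, standard errors, confidence limits and p-values for the interval contrasts and for the 16- and 36-week sums will use the empirical (sandwich) covariance estimator with a small-sample correction and suitable degrees of freedom, in place of Kenward-Roger.*

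The correction and the degrees-of-freedom method should be named and checked at about 50 per arm. Replacing the fallbacks by heterogeneous-variance versions alone is not enough: in one set of assumed courses these still left the 16-week test at 5.7-12.5%.

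The cost is one sentence, a changed procedure option and that check. The estimand, hierarchy and first-choice model are unchanged. There is a small loss of efficiency if a fallback structure happened to be right. With dropout, the sandwich corrects the standard error but not any bias in the point estimate from a wrong covariance; with few missing data expected, that should matter little. Making the change after unblinding would be post hoc.
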